6.1.3 Per-Protocol Cohort

The per-protocol cohort is a subset of the ITT patients who receive a study stent(s) and who do not experience major protocol deviations (ICH E9 definitions).

6.2 Enrollment Controls

The risk of over-enrollment is minimized by utilizing a limited number of clinical centers and maintaining close communication with study centers.

6.3 Withdrawal

All patients enrolled in the clinical study (including those withdrawn from the clinical study or lost to follow-up) shall be accounted for and documented. If a patient withdraws from the clinical investigation, the reason(s) shall be reported. If such withdrawal is due to problems related to investigational device safety or performance, the investigator shall ask for the patients permission to follow his/her status/condition outside of the clinical study.

Reasons for withdrawal include physician discretion, patient choice to withdraw consent, loss to follow-up and death. While study withdrawal is discouraged, patients may withdraw from the study at any time, with or without reason, and without prejudice to further treatment. All applicable case report forms up to the point of patient withdrawal must be completed. Additional data may no longer be collected after the point at which a patient has been withdrawn from the study or withdraws his/her consent, for whatever reason. All open adverse events should be closed or include resolution status. Data collected up to the point of patient withdrawal may be used. Withdrawn patients will not be replaced. Patients who withdraw from the study with the study stent in place will be followed per standard of care at the local institution.

August 28, 2017

Boston Scientific
WallFlex Pancreatic Pivotal Protocol
91067616 Rev/Ver AK
Page 25 of 64

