4.1 Primary Effectiveness Endpoint

Pain Reduction

Pain reduction will be assessed at 6 months post-stent removal or 6 months post-observation of complete or partial stent migration compared to pain collected at baseline. Baseline for patients without a plastic pancreatic stent immediately prior to study stent placement will be at the time of enrollment. Baseline for patients with a plastic pancreatic stent immediately prior to study stent placement will be at the time of study stent placement.

Pain will be scored between 0 and 100 as the mean of the VAS Pain Score and Frequency of Pain sectors of the Izbicki pain scale.

Complete pain relief is defined as pain score ≤ 10 , and partial pain relief is defined as pain score > 10 and reduced by at least 50% compared to baseline.

August 28, 2017

Boston Scientific
WallFlex Pancreatic Pivotal Protocol
91067616 Rev/Ver AK
Page 19 of 64

Complete or partial pain relief in the setting of a 50% higher average daily narcotic dose will be considered a primary effectiveness endpoint failure. Average daily narcotic dosage for prior month will be assessed at baseline visit prior to plastic or study stent placement, whichever is implanted first, and at 6 months post-stent removal/observation of complete distal migration.

Patients who experience stent migration in setting of recurring pain (VAS Pain Score of ≥ 20) will be considered as having failed the primary effectiveness endpoint.

Patients who are restented in the setting of recurring pain will be considered as having failed both the primary effectiveness endpoint and the secondary endpoint for stricture resolution and may only be restented with a non-study stent.

Restenting with a new study stent may only occur during the initial stent placement procedure for such situations as stent misplacement, improper stent size choice, or other conditions, as necessary and will not be considered a primary effectiveness endpoint failure or a secondary effectiveness stricture resolution endpoint failure.

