8.1.2 Hypotheses/Sample Size

Ten (10) articles²⁻¹¹ were identified to be reporting on “pain reduction,” representing 392 evaluable patients. One of these articles¹⁰ did not report on “related SAE rate”; thus, for this endpoint we used 9 articles^{2-9,11}, representing 386 evaluable patients. The table below provides by-publication “pain reduction” and “related SAE” rate used to conduct respective meta-analyses.

Meta-analyses were conducted using a random effects model. The sample sizes were calculated using SAS version 9.4.

Table 8.1.2-1: Pain Reduction and Related SAE Rates by Publication

Study	“Pain Reduction”	“Related SAEs”
Eleftheriadis 2005 ²	62% (62/100)	25% (25/100)
Vitale 2004 ³	83% (62/75)	19% (17/89)
Topazian 2005 ⁴	60% (9/15)	47% (7/15)
Costamagna 2006 ⁵	84% (16/19)	0% (0/19)
Farnbacher 2006 ⁶	55% (53/96)	28% (27/96)
Ishiara 2006 ⁷	78% (7/9)	0% (0/9)
Cahen 2007 ⁸	32% (6/19)	26% (5/19)
Weber 2007 ⁹	82% (14/17)	12% (2/17)
Seza 2011 ¹⁰	85% (17/20)	N/A
Gabrielli 2005 ¹¹	32% (7/22)	32% (7/22)

August 28, 2017

Boston Scientific
WallFlex Pancreatic Pivotal Protocol
91067616 Rev/Ver AK
Page 33 of 64

Pain reduction

For “pain reduction” the meta-analysis yielded a point estimate of 66% with a 95% Confidence Interval (CI) from 53% to 76%.

Statistical testing will be performed to determine if the probability of “pain reduction” when using the WallFlex Pancreatic Stent is greater than the performance goal (PG) set at 53%, the lower bound of the 95% CI from the meta-analysis above. Hence, the following hypothesis will be tested:

$$H_0: \pi_1 \leq 53\%$$

$$H_a: \pi_1 > 53\%$$

where π_1 is the probability of observing “pain reduction”.

Assuming that the observed probability is 75%, 43 patients will be required for the above hypothesis, with a one-sided alpha of 0.025 and power of 80%.

The observed probability of pain reduction was set to 75% given that 8 out of 10 patients in a 10 patient pilot study remained stent free at 6 months post-removal. The primary effectiveness endpoint will be assessed in two ways, namely one using last observation carried forward for patients that are missing 6 month pain data and one counting patients with 6 month pain data as failures. A tipping point analysis will be performed to assess the validity of the associated conclusions.

Related SAEs

For “related SAE rate” the meta-analysis yielded a point estimate of 25% with a 95% CI from 19% to 32%.

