15.1 Anticipated Adverse Device Effects

The following anticipated adverse events (AE) have been identified for this study associated with the placement and removal of the study device.

- Pain
- Cholestasis
- Cholangitis
- Pancreatitis
- Secondary stricture formation
- Obstructive Jaundice
- Vomiting
- Bleeding
- Infection
- Sepsis
- Abscess Formation
- Hyperplastic Tissue Reaction
- Tissue trauma (including events such as duct injury, rupture, edema, inflammation, impaction, laceration and necrosis)
- Pancreatic Duct Rupture
- Allergic Reaction
- Pseudocyst development
- Fever
- Death (excluding disease progression)
- Impaction to pancreatic duct wall
- Perforation with or without pneumoperitoneum
- Pseudoaneurysm

August 28, 2017

Boston Scientific
WallFlex Pancreatic Pivotal Protocol
91067616 Rev/Ver AK
Page 43 of 64

Please refer to the Investigator Brochure for a list of anticipated adverse device effects.

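### The LOCF assessment of pain relief has no exception for patients who die or leave the study because of the device, so it can score them as successes

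*Combined protocol and SAP*

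**What the plan says.** All places are in the combined protocol and SAP.

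- **6.3 Withdrawal.** "Reasons for withdrawal include physician discretion, patient choice to withdraw consent, loss to follow-up and death". After withdrawal, "Additional data may no longer be collected after the point at which a patient has been withdrawn from the study", but "Data collected up to the point of patient withdrawal may be used". Device-driven withdrawal has its own provision: "If such withdrawal is due to problems related to investigational device safety or performance, the investigator shall ask for the patients permission" to follow his or her condition outside the study. The section says nothing about how either kind of patient counts in the analysis. The reason for withdrawal must be reported.
- **8.1.2 Hypotheses/Sample Size, pain reduction.** The primary effectiveness endpoint is assessed in two ways, the first being "one using last observation carried forward for patients that are missing 6 month pain data". The second, as printed, counts as failures those who do have 6-month pain data. This is an evident slip for those who lack it. A tipping-point analysis is added.
- **8.1.3 Sensitivity Analyses.** A missing-equals-failure method is described for the tipping-point analysis, which is optional here but definite in 8.1.2.
- **4.1 and 8.1.1.** Three events override a good pain score. One is a raised narcotic dose: "Complete or partial pain relief in the setting of a 50% higher average daily narcotic dose will be considered a primary effectiveness endpoint failure". The others are stent migration with recurring pain (VAS of 20 or more) and restenting for recurring pain. Death and device-driven exit are not among them.
- **7.1 Data Collection.** Pain is scored at every visit, including Months 1 and 3 with the stent in place.
- **15.1.** Death other than from disease progression is listed among the anticipated adverse events.

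**The concern.** LOCF fills in a value that is supposed to exist but was not observed. For a patient who has died there is no pain score six months after stent removal. For a patient who leaves because of a problem with the device, the exit is itself information about how the device performed. The plan already accepts this principle, since three kinds of bad clinical course override a good pain score. These two are left out, and the LOCF wording has no exception that would catch them.

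So a patient with relief recorded at Month 1 or Month 3, who then dies or withdraws over a device problem, can enter the LOCF numerator as having pain relief six months after removal. The error can only favour the device. It can also make the two assessments disagree because of how a bad outcome is coded, rather than because of true uncertainty about missing scores.

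**Working it through.** **1. Does the text allow it?** Withdrawal stops data collection, so the 6-month score is missing (6.3). Earlier scores exist (7.1) and may be used (6.3). LOCF applies to anyone missing that score (8.1.2). No failure rule intervenes (4.1, 8.1.1). The outcome then depends only on whether the last recorded score meets the definition of relief: 10 or less, or reduced by at least 50% from baseline. The answer is yes.

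**2. The plan's own figure.** Exact one-sided binomial test, performance goal 53%, assumed rate 75%, alpha 0.025. At n = 43 the test rejects at 30 or more successes, with exact alpha 0.0190 and power 83.4%. At n = 42 power is 76.6%. The stated 43 reproduces, and no sample size changes because of this point.

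**3. The decision rule at n = 64** (the planned number meeting the pain criteria at study stent placement, 8.1.2):

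- P(X ≥ 42 | 64, 0.53) = 0.0280, not significant.
- P(X ≥ 43 | 64, 0.53) = 0.0150, significant.

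The cutoff is 43 and the true size is 1.5%. At the planned rate, 0.75 × 64 = 48 successes, a margin of 48 − 43 = 5. It would take six reclassified patients to turn that result into a failure (42/64). At the cutoff, one is enough.

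**4. Type I error if the LOCF result decides.** Let q be the share of patients who die or leave the study because of the device, and s the chance that their carried score counts as relief. Set the true success rate, with these patients as failures, at the 53% goal. LOCF then sees a rate of 0.53 + q·s, and

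type I error = P(X ≥ 43 | 64, 0.53 + q·s).

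The documents give neither q nor s, so both are assumptions. For s, 65–95% is the immediate relief after pancreatic stenting in the European guideline text quoted in 1.1. It describes stented patients generally, so the range is extended down to 30% because those who leave over a device problem may have a poor last score.

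| q | Patients in 64 | s = 30% | s = 65% | s = 95% |
|---|---|---|---|---|
| 0 | 0 | 1.5% | 1.5% | 1.5% |
| 1% | 0.64 | 1.7% | 1.9% | 2.2% |
| 2% | 1.28 | 1.9% | 2.5% | 3.1% |
| 3% | 1.92 | 2.1% | 3.2% | 4.3% |
| 5% | 3.2 | 2.7% | 4.9% | 7.9% |

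Example: q = 3%, s = 95% gives 0.53 + 0.03 × 0.95 = 0.5585, and P(X ≥ 43 | 64, 0.5585) = 0.043.

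Because the exact test starts at 1.5%, a 1% share stays below the nominal 2.5% throughout the range. At 2% the excess is small and needs a carried-success chance above about 65%.

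**The case against.** The strongest objection is that the plan already has an assessment that handles these patients. With the misprint in 8.1.2 read as missing counted as failure, which 8.1.3 supports, every death and every device-driven exit is a failure there, and the tipping-point analysis pushes the same way. This stands: if that assessment decides, none of the inflation above arises. It does not close the point, because the plan does not name the deciding assessment, the safeguard is misprinted, and the tipping-point analysis is definite in one section and optional in another.

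Three stronger readings are tempting, and the documents do not support them.

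- *That section 6.3 is itself in error, or treats device withdrawals like all others.* It deals with patient accountability and gives device withdrawals a separate follow-up provision. The operative gap is in 8.1.2 and in the failure rules.
- *That every device problem leads to a false success.* Section 4.5 allows early stent removal for pain, and 7.12 follows patients for six months after initial removal. Such patients can stay in the study and have a 6-month score. Restenting with recurring pain and migration with recurring pain are failures already. A patient who leaves with high recorded pain also fails under LOCF.
- *That the trial's error rate is badly inflated.* That needs event shares of 5% or more and a high carried-success chance. The 10% allowance in 8.1.2 covers all losses, not only these. In the 10-patient pilot (1.2), none of the seven serious adverse events listed was a death, and no stent was removed for intolerable pain. Ten patients cannot exclude higher rates, but they do not support a large one.

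It is also true that a related serious event, including one that ends in death, counts in the primary safety endpoint. That does not stop the same patient counting as an effectiveness success.

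**Conclusion.** The gap is real and narrow. As written, the LOCF assessment can score as a pain-relief success a patient who died or left the study because of the device. It affects only the LOCF assessment, and only patients who leave the study before the 6-month score.

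The size cannot be fixed from the documents. If LOCF decides, with 64 patients analysed and a carried-success chance of 30–95%, type I error runs from 1.7–2.2% at a 1% share to 2.7–7.9% at 5%, against a nominal 2.5%. At shares of 1–2% there is little or no excess. The case for acting rests on the direction of the error, which always favours the device, and on the ease of settling the coding before results are seen.

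**What to change.** In 8.1.1 and 8.1.2, with matching text in 4.1 and the synopsis, state: patients who die, or who withdraw from the study because of problems with device safety or performance, before the 6-month assessment count as primary effectiveness failures in both assessments; LOCF applies only to other patients missing 6-month pain data.

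In the same edit, correct the misprint in 8.1.2 so that the second assessment counts patients *missing* 6-month pain data as failures, and say which of the two assessments decides the hypothesis test.

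The cost is one sentence and one line of code. No visit, data item or sample size changes, since 6.3 already requires the reason for withdrawal. There are two downsides. The LOCF success rate may come out slightly less favourable. The device-withdrawal category also relies on the reason the investigator reports, which is a judgement that a pure missing-as-failure rule avoids.

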6.4 End of Study Action Plan

Patients will have the study device, the WallFlex Pancreatic Stent, implanted temporarily for up to six months. Per section 7.11, a patient will be considered lost to follow-up if the patient remains unresponsive to communication after three documented attempts by study staff. However, for those patients who remain unresponsive to communication while the stent remains in place, additional attempts will be made to request the patient's return for study stent removal. These additional attempts may include increased telephone and written communications and contact with the patient's primary care physician (if this communication is consented to in the Informed Consent Form).

August 28, 2017

Boston Scientific
WallFlex Pancreatic Pivotal Protocol
91067616 Rev/Ver AK
Page 26 of 64

7 Study Methods

7.1 Data Collection

Procedure/Assessment	Screening/ Baseline	Study Stent Placement****	Month 1 (30 ± 5 Days)	Month 3 (90 ± 10 Days)	Month 6 Study Stent Removal (180 ± 15 Days)	Month 3 Post-Removal Follow-up Visit (90± 15 Days)	Month 6 Post-Removal Follow-Up Visit (180 days ± 15 days)
Informed consent form, including informed consent signature date	X						
Demographics and Medical and EPS History	X						
Weight*	X	X	X	X	X	X	X
EPS		X (if required)					
Pre-stenting pancreatic stone clearance (as applicable)	X***	X					
Study Stent Placement		X					
Study Stent Removal					X		
Pancreatic Duct Imaging (may be non-invasive)	X***	X Pre- and Post- Stent Placement			X** Post-Stent Removal		X
Pain Score, Average Daily Narcotic Dose, and QOL Score*	X	X (prior to all stent procedures)	X	X	X (prior to stent removal)	X	X
Adverse Event Assessment	X***	X	X	X	X	X	X
Concomitant Medications, including injectable narcotics	X	X	X	X	X	X	X

* Weight Pain Score and QOL must be assessed at all visits, including any unscheduled visits.

**Window for imaging is ±4 weeks.

***Applicable at Baseline visit for patients who undergo plastic stent placement for ESWL per inclusion criteria 9.

****Study Stent Placement visit may take place on the same day as Screening/Baseline, if deemed appropriate by the treating physician

Boston Scientific
WallFlex Pancreatic Pivotal Protocol
91067616 Rev/Ver AK
Page 27 of 64

August 28, 2017

7.2 Study Candidate Screening

No study-specific testing will be conducted until after the patient has signed an ICF. A Screen Failure/Enrolled Log will be maintained in Electronic Data Capture (EDC) by the center to document select information about candidates who signed consent.

7.3 Informed Consent

Written Informed Consent must be obtained for all patients who are potential study candidates. Patients will be asked to sign the Informed Consent form before any study-specific tests or procedures are performed. The Informed Consent form is study-specific and must be approved by the study Institutional Review Board (IRB)/Ethics Committee (EC) and Competent Authority, as applicable. Study personnel should explain that even if a patient agrees to participate in the study and signs the ICF, the ERCP procedure may demonstrate that the patient is not a suitable candidate for the study.

7.4 Scoring System

7.4.1 Izbicki Scoring System

The Izbicki Pain Scale incorporates four elements: 1) patient self-estimation of intensity of pain using a visual analog scale (VAS), 2) the frequency of pain attacks, 3) analgesic medication usage and 4) the time periods of inability to work. The sum of the rank values divided by four gives the final value of the pain score. See Appendix 22.1 for the Pain Scale.

Patients will be asked to report on the average pain experienced since the prior visit when reporting pain via VAS for the first element of the Izbicki Pain Scale. Patients will be asked to report the average frequency of pain attacks experienced since the prior visit for the second element of the Izbicki Pain Scale. Please see Appendix 22.5 for further guidance on collecting the VAS and frequency of pain attacks information.

Note: For centers with medication types that do not align with section 3 of the Izbicki Pain scale, relevant corresponding medication types may be made available for scoring.

7.4.2 SF-12

The SF-12 (Short Form 12 Item Survey), see Appendix 22.2, is a twelve question survey based off the larger SF-36 scoring system that assesses overall health-related quality of life. The SF-12 is weighted and summed to provide scales for physical and mental health.

7.4.3 Average Daily Narcotic Dosage

Average Daily Narcotic Dose for the previous month will be calculated for all study patients at all study visits. The value for this data point will be expressed in units of morphine milligram equivalents (MME).

August 28, 2017

Boston Scientific
WallFlex Pancreatic Pivotal Protocol
91067616 Rev/Ver AK
Page 28 of 64

Site personnel will collect narcotic use information as part of concomitant medication data collection at each visit. Documentation of all narcotic dosage increases and/or decreases throughout the patient's participation will be very important for the accurate calculation of Average Daily Narcotic Dose.

Site personnel will convert all daily narcotic dosages for the previous month to MME. The daily MME values obtained will be added together and divided by the number of days in the previous month to obtain the Average Daily Narcotic Dose. The Average Daily Narcotic Dose value will be rounded to the nearest whole number, if necessary.

Please see Appendix 22.4 for examples of Average Daily Narcotic Dosage calculations.

7.5 Screening/Baseline – Office/Hospital Visit

- Informed Consent
- Eligibility Criteria Assessment
- Demographics
- Medical and EPS History
- Pain Score
- Concomitant Medications (including injectable narcotics)
- Average Daily Narcotic Dose for Prior Month
- Weight
- Quality of Life
- EPS History
- Plastic Stent Placement, as applicable per inclusion criteria 9
- Imaging, as applicable
- Adverse Event/Device Event Assessment, as applicable

7.6 WallFlex Pancreatic Study Stent Placement – Office/Hospital Visit

- May be performed on the same day as Screening/Baseline visit, if deemed appropriate by the treating physician

7.6.1 Stent Size Selection

- If the upstream dilated pancreatic duct is \leq 6 mm, a 6 mm diameter WallFlex Pancreatic stent should be placed.
- If the upstream dilated pancreatic duct is $>$ 6 mm, an 8 mm diameter WallFlex Pancreatic stent should be placed.

7.6.2 Assessments

- Pain Score (prior to stent procedures)
- Weight
- Concomitant Medications (including injectable narcotics)
- Average Daily Narcotic Dose for Prior Month

August 28, 2017

Boston Scientific
WallFlex Pancreatic Pivotal Protocol
91067616 Rev/Ver AK
Page 29 of 64

- Quality of Life
- Pancreatic Duct Imaging (pre-and post-procedure)
- EPS (if required, per section 2.2)
- Plastic Stent Removal prior to study stent placement, as applicable
- Study Stent Placement Procedure
- Adverse Event/Device Event Assessment

7.7 *Stent Indwell Follow-Up: Month 1 (30 days ± 5 days) and Month 3 (90 days ± 10 days) – Telephone or Office/Hospital Visit*

- Pain Score
- Concomitant Medications (including injectable narcotics)
- Average Daily Narcotic Dose for Prior Month
- Weight
- Quality of Life
- Adverse Event/Device Event Assessment

7.8 *Study Stent Removal Visit: Month 6 (180 days ± 15 days) – Office/Hospital Visit*

- Pain Score (prior to stent removal)
- Concomitant Medications (including injectable narcotics)
- Average Daily Narcotic Dose for Prior Month
- Weight
- Quality of Life
- Study Stent Removal
- Adverse Event/Device Event Assessment
- Pancreatic Duct Imaging
- OPTIONAL: Pancreatogram 24-72 hours post-stent removal, in case a naso-pancreatic drain was left in place after stent removal.

7.9 *Post-Stent Removal Follow-Up: Month 3 (90 days±15 days post-removal) – Telephone or Office/Hospital Visit*

- Pain Score
- Concomitant Medications (including injectable narcotics)
- Average Daily Narcotic Dose for Prior Month
- Weight
- Quality of Life
- Adverse Event/Device Event Assessment

7.10 *Post-Stent Removal Follow-Up: Month 6 (180 days±15 days post-removal) – Telephone or Office/Hospital Visit*

- Pain Score
- Concomitant Medications (including injectable narcotics)

August 28, 2017

Boston Scientific

WallFlex Pancreatic Pivotal Protocol

91067616 Rev/Ver AK

Page 30 of 64

- Average Daily Narcotic Dose for Prior Month
- Weight
- Quality of Life
- Adverse Event/Device Event Assessment
- Pancreatic Duct Imaging

